Participants: Ages between 18 and 75. n=15 subjects with SCI. n=15 able-bodied volunteers.

Inclusion criteria

Able-bodied participants

1. Age between 18 and 75 years; n=15 for both Aims;
2. No known central or peripheral neurological disease or injury.

SCI participants

1. Age between 18 and 75 years; n=15 for Aims 1 and 2;
2. Chronic (> 12 months) motor-incomplete SCI between neurological levels {C1-C8};
3. Score of 2, 3, or 4 (out of 5) on manual muscle testing of wrist extension, wrist flexion, finger extension, finger flexion, or finger abduction in left or right hand;
4. Detectable F-wave responses of the left or right APB to median nerve stimulation and/or FDI to ulnar nerve stimulation;

Exclusion criteria

1. Multiple spinal cord lesions;
2. History of seizures;
3. Ventilator dependence or patent tracheostomy site;
4. Use of medications that significantly lower seizure threshold, such as tricyclic antidepressants, amphetamines, neuroleptics, dalfampridine, and bupropion;
5. History of stroke, brain tumor, brain abscess, or multiple sclerosis;
6. History of moderate or severe head trauma (loss of consciousness for greater than one hour or evidence of brain contusion or hemorrhage or depressed skull fracture on prior imaging);
7. History of implanted brain/spine/nerve stimulators, aneurysm clips, ferromagnetic metallic implants, or cardiac pacemaker/defibrillator;
8. Significant coronary artery or cardiac conduction disease;
9. Recent history (within past 6 months) of recurrent autonomic dysreflexia, defined as a syndrome of sudden rise in systolic pressure greater than 20 mm Hg or diastolic pressure greater than 10 mm Hg, without rise in heart rate, accompanied by symptoms such as headache, facial flushing, sweating, nasal congestion, and blurry vision (this will be closely monitored during all screening and testing procedures);
10. History of bipolar disorder;
11. History of suicide attempt;
12. Active psychosis;
13. Heavy alcohol consumption (greater than equivalent of 5 oz of liquor) within previous 48 hours;
14. Open skin lesions over the face, neck, shoulders, or arms;
15. Pregnancy
16. Unsuitable for study participation as determined by study physician.

Recruitment:

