Potential participants will be encouraged to ask questions throughout the process. Potential participants will be informed of their right to withdraw at any time and that choosing to not participate will not infringe on any of their regular VA benefits or medical care. Once he/she has no further questions and the study team is confident that the potential participant fully understands the protocol and its risks, then the participant will be asked whether he or she is willing to sign the ICF.

Procedures:

General: All procedures are performed in a seated position with elbows at roughly 90 degrees and hands resting on a pillow in pronated position. Electrophysiological measurements are made using the dominant or stronger affected arm. Safety (blood pressure, heart rate, pulse oxygenation, peak expiratory flow rate, and structured symptom questionnaire) and tolerability are closely monitored throughout all experiments (see Human Subjects section).

Electromyography (EMG): EMG is recorded using surface sensors with 300x preamplification, 15-2,000 Hz bandwidth, and internal grounding (Motion Lab Systems). EMG input is collected at a sample rate of 5,000 Hz via digital acquisition board and customized LabVIEW software (National Instruments). Muscles recorded may include abductor pollicis brevis (APB), abductor digiti minimi (ADM), first dorsal interosseous (FDI), flexor carpi radialis (FCR), extensor carpi radialis (ECR), and/or biceps brachii.

TMS: TMS is performed using a MagPro X100 stimulator (MagVenture). The hand motor cortex ‘hotspot’ is found while monitoring EMG motor response. Location of the hotspot and all subsequent TMS stimuli are tracked using a neural navigation system (Brainsight). Resting motor threshold is determined by delivering pulses with increasing intensity until motor responses of $\geq 50\text{ }\square\text{V}$ are observed in the APB or FDI muscle in at least 5 out of 10 stimuli.

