CES: CES is performed using two DS7A nerve stimulators or a dual DS8R stimulator (Digitimer) linked to deliver biphasic pulses (1 ms each phase; cathodal first). The cathode is a 5x10 cm surface electrode (Natus) placed longitudinally with the top edge ~2.5 cm caudal to the C7 spinous process (~T1-T3 vertebral levels posteriorly). The 5 x 10 cm anode is placed horizontally over the thyroid cartilage, corresponding to the C4-C5 levels anteriorly. Two 5x10 cm common ground electrodes are placed over the distal clavicles. Stimulus intensity ranges from 0-80 mA. Motor threshold is determined analogously to the method used in TMS. Blood pressure, heart rate, pulse oximetry, and peak expiratory flow rate are monitored every three minutes.

Peripheral nerve stimulation: Stimulation is delivered using a DS7A or a DS8R nerve stimulator and dual surface electrodes (20 mm apart). M-wave and F-reflex responses are triggered over the median and ulnar

nerves at the wrist, recording over the APB and FDI muscles, respectively. F-wave pulse intensity is ~110-120% of the intensity that results in maximal compound motor action potential (CMAP). H-reflex responses are triggered over the median nerve at the elbow, recording over the FCR muscle. H-reflex pulse intensity will be calibrated to result in H-reflex amplitude ~20-25% of maximal CMAP⁶³. Pulse width is 0.2 ms for M/F wave stimulation and 1.0 ms for H-reflex stimulation.

Timing: Peripheral motor conduction time is calculated using F-wave and M-wave latencies using the formula $(\text{Latency}_M + \text{Latency}_F - 1) \div 2$ ⁶⁴. Central motor conduction time is calculated as the TMS-evoked potential latency minus the peripheral conduction time. These values are used to precisely synchronize arriving TMS, CES, and peripheral pulses at cervical motor neurons in the relevant experiments.

Replication: For Aim 1, testing will occur over three sessions. For Aim 2, testing will occur over two sessions. This will allow confirmation of key intensity and timing parameters defined for each subject over different sessions, improving reliability of the findings.

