- Interpretation: These experiments will lead to multiple insights. Through segmental interactions, confirmation of Hypothesis 1.2 would further demonstrate the ability of CES to positively modulate motor neuron excitability, and confirmation of hypothesis 1.3 would indicate the potential for CES to reduce spasticity⁴⁵. Confirmation of speculative hypothesis 1.2 would demonstrate that at high intensity, CES pulses travel via efferent nerve roots and collide with retrogradely traveling F-waves.

Aim 1 data analysis: Peak-to-peak amplitude of all conditioned pulses will be normalized to the amplitude of unconditioned pulses. For each interaction paradigm, analysis of variance (ANOVA) with factors of subject group, stimulus intensity, interstimulus interval, and muscle will be performed. Post hoc pairwise comparisons will be made using Tukey’s method. *Power:* Using a conservative predicted effect size of 0.4 for each interaction paradigm, >80% power will be achieved with a sample size of 10 for each analysis (repeated measure ANOVA) with four factors. 15 subjects in each group (SCI, able-bodied) will undergo testing.

Aim 1 Timeline (Table 2):

Each subject will undergo three testing sessions on separate days, with a minimum of 24 hours and a maximum of two weeks between visits. Per subject, Aim 1 participation would therefore take 3 to 28 days. 30 subjects will be enrolled, resulting in 90 total testing sessions. A conservative projection of completing two testing sessions per week would result in a timeline of 45 weeks or 11-12 months for completing Aim 1.

Aim 2: Determine optimal CES parameters for acutely facilitating concurrent wrist and hand movements.

Volitional limb movements depend on the same corticospinal and spinal motor circuits as those activated by TMS and F-waves. Therefore, since preliminary data shows that subthreshold CES facilitates TMS responses, CES may also be able to facilitate volitional limb movements. The experiments in Aim 2 will shed light on this clinically applicable question.

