Interpretation: Confirmation of Hypothesis 2.1 would substantiate the predicted findings of Hypotheses 1.1 and 1.2 and our early preliminary data that indicate CES’s ability to positively modulate corticospinal and/or motor neuron excitability. We expect optimal facilitation when subthreshold CES is delivered at closer to motor threshold intensity. We do not know whether the effects will differ depending on intensity of volitional effort, but if so, further experiments could investigate the roles played by peripheral, spinal, and supraspinal components of effort intensity⁶⁹. Furthermore, these experiments would shed light on whether CES modulates ongoing motor neuron activity differently at different spinal levels during level-specific motor tasks (thumb-finger opposition C8-T1, wrist extension C6). Most importantly, confirmation of Hypothesis 2.1 would represent an opportunity to directly translate and test this paradigm for clinical benefit by combining repetitive subthreshold CES with repetitive task-oriented physical exercise training.

If high-intensity CES inhibits concurrent volitional activity as predicted by Hypothesis 2.2, this would be analogous to the ‘cortical silent period’ (CSP) noted when cortical TMS is delivered during volitional contraction^{5,6}. The early phase of CSP (the first 50-75 ms after onset of the cortical motor-evoked potential) is mediated by poorly understood spinal mechanisms⁵. Our observations of the onset and duration of a ‘spinal silent period’ (SSP) in response to CES would shed mechanistic light on this phenomenon.

Aim 2 Data analysis: Rather than peak-to-peak amplitude, the effects of CES on concurrent volitional muscle contraction will be measured using RMS as described above. Repeated-measure ANOVA with factors of subject group, volitional effort intensity, CES intensity, post-stimulus timebin, and muscle will be performed. Post hoc pairwise comparisons will be made using Tukey’s method. Although we can only speculate on the predicted effect size, with use of a conservative effect size of 0.4 for each interaction paradigm, >80% power will be achieved with a sample size of 10 for each analysis (repeated measure ANOVA with five factors). 15 subjects in each group (SCI, able-bodied) will undergo testing.

Aim 2 Timeline:

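### Some SCI participants can have absent or undefined muscle cells, which a repeated-measures ANOVA with muscle as a factor cannot use, and the plan does not say how these are handled

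*Combined protocol and SAP*

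**What the plan says.** All references are to section 3 of the combined protocol and SAP.

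- **Eligibility (SCI inclusion criterion 4).** One muscle on one side is enough: "Detectable F-wave responses of the left or right APB to median nerve stimulation and/or FDI to ulnar nerve stimulation".
- **Arm measured (Procedures, General).** "Electrophysiological measurements are made using the dominant or stronger affected arm". This need not be the arm that met criterion 4.
- **Muscles (Procedures, EMG).** The list is permissive: "Muscles recorded may include abductor pollicis brevis (APB", followed by five others.
- **TMS threshold (Procedures, TMS).** Resting threshold is reached when responses appear in APB or FDI. Test pulses are then given at 120% of threshold (CES-TMS interactions).
- **Aim 1 outcome and model (Aim 1 data analysis).** Conditioned amplitudes are divided by the unconditioned amplitude. For each interaction paradigm, an ANOVA with "factors of subject group, stimulus intensity, interstimulus interval, and muscle will be performed". The power sentence calls this a repeated-measures ANOVA with four factors and claims more than 80% power at effect size 0.4 with a sample size of 10.
- **H-reflex (Procedures, Peripheral nerve stimulation).** "H-reflex responses are triggered over the median nerve at the elbow, recording over the FCR muscle".
- **Aim 2 model (Aim 2 Data analysis).** "Repeated-measure ANOVA with factors of subject group, volitional effort intensity, CES intensity, post-stimulus timebin, and muscle".

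The text available for review contains no rule for a muscle that does not respond, no missing-cell rule and no mixed model.

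**The concern.** A classical repeated-measures ANOVA needs a value in every within-person cell. The rules above let a participant lack one in two ways. A muscle may not be recorded. Or it may be recorded but give no unconditioned response, and then the Aim 1 ratio has a zero denominator.

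Criterion 4 applies only to the SCI group, and absent responses are more likely where conduction is impaired. Losses would therefore be expected in the SCI group and probably among its more impaired members. Aim 1 expects reduced CES-TMS facilitation in SCI compared with uninjured subjects. If the analysed SCI participants are those with more preserved responses, that comparison is exposed to selection as well as to loss of power.

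The H-reflex model is a separate fault of specification: a factor with one level cannot be estimated.

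**Working it through.** **1. The plan's own power figure.** From the plan: effect size f = 0.4, N = 10. Assumed, because not stated: alpha 0.05, correlation between repeated measures ρ = 0.5, sphericity, and four factors read as m = 4 measurements. For a within-person effect in one group:

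λ = f²·N·m/(1−ρ) = 0.16 × 10 × 4/0.5 = 12.8, with df 3 and 27.

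Power is 80.6%, which agrees with the stated figure. It depends on ρ: 48.3% at ρ = 0, 64.9% at 0.3 and 96.3% at 0.7.

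**2. Where cells can go missing or undefined, by paradigm.**

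| Paradigm | Outcome | Muscle cell absent or undefined? |
|---|---|---|
| CES-TMS | amplitude ratio | Yes, if the second muscle is silent at 120% of a threshold set on the other, or is not recorded |
| CES-F | persistence out of 25 | No for a recorded muscle; silence scores 0% |
| CES-F | amplitude ratio, if analysed | Yes, if there is no unconditioned F-wave |
| CES-H | amplitude ratio, FCR only | No second muscle exists; the muscle factor has one level |
| Aim 2 | RMS over baseline RMS | Only if the muscle is not recorded |

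**3. How many complete SCI cases might remain.** Let q be the share of SCI participants with one usable muscle. The documents do not give q, so the values below are illustrations. Complete cases C ~ Binomial(15, 1−q); the expected number is 15(1−q); the risk is P(C ≤ 9).

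| q | Expected complete | P(fewer than 10) |
|---|---|---|
| 10% | 13.5 | 0.2% |
| 20% | 12.0 | 6.1% |
| 30% | 10.5 | 27.8% |
| 33% | 10.05 | 37.1% |
| 40% | 9.0 | 59.7% |
| 50% | 7.5 | 84.9% |

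**4. What the loss does to power** (f = 0.4, alpha 0.05, ρ = 0.5).

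| Effect | 15 complete SCI | 10 complete SCI |
|---|---|---|
| Within SCI, four levels | 95% | 81% |
| Within SCI, two levels (such as APB vs FDI) | 82% | 62% |
| Group main effect, four measurements, 15 able-bodied | 76% | 66% |

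The margin of 15 over 10 absorbs five losses for a four-level within-SCI effect. It does not for the muscle contrast, and the group main effect is under 80% even with all 15.

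**5. Behaviour of the two methods.** Take 15 people, 2 muscles and 4 intervals, with 5 people lacking one muscle. The full layout has 15 × 2 × 4 = 120 cells, of which 120 − 5 × 4 = 100 are observed. A complete-case repeated-measures ANOVA keeps 10 people and 10 × 8 = 80 cells, so 20 valid observations are discarded. The statsmodels repeated-measures routine, given all 100 cells, stopped with an unbalanced-data error. A mixed model used all 15 people and all 100 cells.

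**The case against.** The strongest reply is that criterion 4 concerns F-waves, and the outcome named for F-waves in Hypothesis 1.2 is persistence. A silent muscle scores 0 out of 25, which is a defined floor value. An absent F-wave also does not show an absent TMS response. This stands. The persistence analysis loses no cell in this way; the CES-TMS gap comes from the threshold rule, the open muscle list and the ratio.

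A reader might also infer three wider faults, none of which the documents support:

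- **Missing Aim 2 tasks.** Criterion 3 can be met on a single movement ("Score of 2, 3, or 4 (out of 5) on manual muscle testing of wrist extension, wrist flexion, finger extension" and two others). But it is a weakness criterion and says nothing about the remaining movements. Task is not a factor in the Aim 2 ANOVA, and an RMS ratio can be computed for any recorded muscle.
- **The current ceiling.** "Stimulus intensity ranges from 0-80 mA", and 80/1.75 = 45.7 mA, so a higher threshold would rule out 175% of threshold. But 30-175% is a range, not a level required of everyone, CES-TMS stops at 95%, and no thresholds in mA are given in the available text.
- **Certain loss of whole participants.** The plan states no complete-case rule, and for Aim 1 the repeated-measures label appears only in the power sentence. Software may stop rather than drop people.

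It is also fair that the sample size of 10 is not said to be per group, so using it as a floor for the SCI group is one reading. The H-reflex fault costs no participant; it is a correction to the model.

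What remains is that the plan permits undefined cells, names a method that cannot take them, and gives no rule.

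**Conclusion.** The point holds in a limited form. Absent or undefined muscle cells are possible in SCI participants, chiefly for CES-TMS amplitude and any F-wave amplitude analysis. The stated ANOVA would then either exclude those participants or not run. The muscle factor cannot be fitted for the H-reflex.

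The size cannot be derived from the documents. The risk of fewer than 10 complete SCI cases runs from negligible (0.2% at a 10% share) to more likely than not (60% at a 40% share). It rests on an assumed share, on independence between participants and on reading 10 as an SCI-group number. The power figures also rest on the assumed alpha, correlation and number of levels. That the loss would fall on the more impaired is a reasonable inference, not something the documents show. The change is worth making because it is cheap and should be settled before data are seen.

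**What to change.** 1. Replace the repeated-measures ANOVA in both Aims with a linear mixed model: random intercepts for participant and for session within participant, small-sample degrees of freedom, all available cells kept.
2. Fix the muscle set for each paradigm.
3. Analyse amplitude on a scale defined for non-responders, for example conditioned amplitude with the unconditioned amplitude as a covariate, or state how an absent unconditioned response is scored. A mixed model alone is not enough, because it cannot use a ratio with a zero denominator.
4. Omit the muscle term for the H-reflex.
5. Report participants and cells by paradigm and group.

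The cost is SAP wording, analysis code and some extra modelling work, with no new data or participants. The model assumes that missing cells are missing at random given what is observed. That may be doubtful if muscles are absent because of severity, so the counts in item 5 should be read alongside the estimates.

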As opposed to stimulation configuration and pairing with other modalities, the effect of timing between successive spinal cord stimuli has received less attention in comparison to similar experiments in the field of TMS. Extensive studies have defined rTMS effects over a range of pulse frequencies and patterns, in a broad variety of injury and disease contexts. A similarly rigorous definition of spinal stimulation timing effects has not yet been achieved. One reproducible finding has shown that at low suprathreshold intensities, a conditioning spinal pulse inhibits a second spinal pulse given 20-50 ms later^{1,44,45,60}. These findings, which we have confirmed in our own studies, indicate that at these intensities, spinal stimulation triggers afferent sensory fibers that activate motor neurons via synapses that are subject to homosynaptic depression. However, these studies need to be supplemented with experiments that more deeply investigate basic mechanisms of circuit interactions. In the TMS field for example, conditioning pulses inhibit test pulses given either 1-3 or 100-200 ms later, and facilitate test pulses given 8-15 ms later. The effects of these time intervals have revealed important brain circuit interactions termed short-interval cortical inhibition (SICI), long-interval cortical inhibition (LICI), and intracortical facilitation (ICF), respectively^{18,21}. Using conditioning and test stimuli over a broad range of time intervals, site, and modality combinations, we now expect to define similar types of circuit interactions mediating the response to CES.

Our team is optimally positioned to address these gaps – we already conduct studies involving electrical and magnetic stimulation in a well-run clinical research center; and we have already obtained FDA and IRB clearance to conduct human studies using our novel CES technique.

PRELIMINARY DATA

Non-invasive, non-noxious cervical electrical stimulation (CES)

One 5x10 cm electrode is placed longitudinally over the midline with the top edge 2 cm caudal to the C7 spinous process (~T1-T3 vertebral levels). Another 5x10 cm electrode is placed horizontally centered over the thyroid cartilage, corresponding to the C4-C5 levels anteriorly (**Figure 1**). Two 5x10 cm common

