Figure 2. CES activates multiple muscles simultaneously. **A)** CES waveforms in one non-disabled volunteer depicted in raster format. CES stimulus at ~200% threshold. Note the proximal to distal gradient of latencies and amplitudes. **B)** Intensity-response curves of five different arm muscles, showing distal muscle selectivity. **C)** CES symmetrically activates homologous muscles on both sides 10 non-disabled subjects. **FCR**, flexor carpi radialis; **ECR**, extensor carpi radialis; **ADM**, abductor digiti minimi; **APB**, abductor pollicis brevis.

CES targets different circuits at different intensities

At peri-threshold intensity, latencies to the APB muscle are up to ~3-5 ms longer than the peripheral motor conduction time (not shown). At higher stimulation intensities, latency is equal to or shorter than the peripheral motor conduction time. Similar observations have been made in studies of other transcutaneous spinal stimulation paradigms^{43,61,62}. These findings are consistent with lower intensity stimuli acting via

[figure not shown]
afferent sensory fibers that synapse onto lower motor neurons, and higher intensity stimuli acting via efferent motor fibers ~2-4 cm distal to the cell bodies. The longer route traversed by lower-intensity stimuli explains the longer latency.

These afferent versus efferent root transmission pathways are further demonstrated by the response to two sequential CES pulses given 40 ms apart (**Figure 3**). At low intensity, the amplitude of the second pulse is strongly reduced, suggesting post-activation synaptic depression as seen with H-reflexes and posterior root-muscle reflexes^{1,44,45,60}. At high intensity, there is little to no decrement, suggesting direct efferent fiber axonal activation, which is not susceptible to post-activation depression.

Subthreshold CES acutely facilitates muscle responses to cortical stimulation

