- Interpretation: If subthreshold CES facilitation occurs at ISI between 2-20 ms, this would support the mechanism of heterosynaptic summation between segmental Ia input and descending corticospinal input¹. If facilitation occurs at ISI between 20-60 ms, this would support the mechanism of sensory cortical facilitation of motor cortex excitability (based on analogous findings using peripheral nerve stimulation^{4,2,3}). Because TMS travels along the same corticospinal and subcortical circuits used during volitional movement, this would also set the basis for using subthreshold CES to facilitate motor

responses during physical training programs (see Aim 2). Subjects with incomplete cervical SCI are expected to have reduced CES-TMS facilitation compared to uninjured subjects (see **Figure 4**).

CES-peripheral nerve interactions:

- Goal: Measure interactions between afferent and efferent cervical nerve roots, segmental interneuronal circuits, orthodromically conducting peripheral sensory fibers, and antidromically conducting peripheral motor fibers.
- Methods: F-wave pulse intensity will be ~110-120% of the intensity that results in maximal compound motor action potential (CMAP). H-reflex pulse intensity will be calibrated to result in H-reflex amplitude ~20-25% of maximal CMAP⁶³. Conditioning CES pulse intensity will be set between 30-175% of motor threshold, delivered within 300 ms of test pulses. For subthreshold conditioning CES, either single or “theta bursts” (3 pulses at 50 Hz)¹⁹ will be delivered. All pulse combinations will be delivered at a rate of 0.1 Hz, in pseudorandom parameter order, until 8 (CES-H combinations) or 25 (CES-F combinations) responses per parameter have been recorded.
- Hypothesis 1.2: Conditioning CES will increase persistence (number of responses per 25 stimuli) of median (APB) and ulnar (FDI) F-responses elicited up to 50 ms later.
- Hypothesis 1.3: Conditioning CES will reduce amplitude of median (FCR) H-responses elicited up to 50 ms later.
- Speculative hypothesis 1.2: Conditioning suprathreshold CES will block spinal motor neuron F-responses delivered up to 10 ms later.

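### An F-wave block within 10 ms of suprathreshold CES shows that CES fired those motor axons; it does not by itself demonstrate the efferent-root route

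*Combined protocol and SAP*

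**What the plan says.** Aim 1, CES-peripheral nerve interactions, lists as speculative hypothesis 1.2: "Conditioning suprathreshold CES will block spinal motor neuron F-responses delivered up to 10 ms later". The Interpretation that follows says that confirmation "would demonstrate that at high intensity, CES pulses travel via efferent nerve roots and collide with retrogradely traveling F-waves". The Methods there give the available settings: "Conditioning CES pulse intensity will be set between 30-175% of motor threshold, delivered within 300 ms of test pulses". No list of intervals is given, and neither a criterion for a block nor a numerical limit for high intensity is stated.

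Two earlier parts of the document describe the other route. The section on gaps in mechanistic understanding says of low suprathreshold pulses that "at these intensities, spinal stimulation triggers afferent sensory fibers that activate motor neurons via synapses that are subject to homosynaptic depression". The Preliminary Data report that, at peri-threshold intensity, "latencies to the APB muscle are up to ~3-5 ms longer than the peripheral motor conduction time". They contrast this with "higher intensity stimuli acting via efferent motor fibers ~2-4 cm distal to the cell bodies".

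**The concern.** Collision needs only an orthodromic impulse in the motor axon when the antidromic volley from the wrist arrives. An axon excited at the root carries such an impulse. So does the axon of a motor neuron fired through afferents and a synapse. The plan accepts that both happen above motor threshold, and the hypothesis is worded for suprathreshold CES generally. If both routes predict a block at the same intervals, observing one says that CES fired those axons and leaves the route open.

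Aim 1 sets out to map the cellular and synaptic targets of CES, and the contrast between afferent and efferent roots is central to how the document describes the technique. As the Interpretation stands, a block at an intensity where reflex firing contributes would be reported as demonstrating efferent transmission.

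**Working it through.** **Inputs from the documents.**
- Procedures, Timing: "Peripheral motor conduction time is calculated using F-wave and M-wave latencies using the formula" P = (M + F - 1) / 2, where M and F are the M-wave and F-wave latencies.
- Peripheral nerve stimulation: "M-wave and F-reflex responses are triggered over the median and ulnar" nerves at the wrist, recorded at APB and FDI.
- Preliminary Data: the extra delay of the afferent route is up to about 3-5 ms; the efferent site is about 2-4 cm beyond the cell bodies.

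**Assumed inputs (the documents give no values).** F 24-32 ms, M 3-4.5 ms, motor conduction velocity 50-65 m/s.

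**The plan's own figure.** The 10 ms limit cannot be reproduced without F and M latencies. Under the assumptions it falls within the range at which efferent collision would end (table below), so it is a plausible figure for that route.

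**Method.** Wrist-to-cord time is W = P - M = (F - M - 1) / 2. Put CES at time 0 and the wrist shock at time d. A motor volley that leaves the cord at t0 collides with the antidromic volley if d < t0 + W and d + W > t0.
- Efferent: the volley starts 2-4 cm down the axon, a lead of 0.02/65 s = 0.31 ms to 0.04/50 s = 0.80 ms. Collision ends at W - 0.80 to W - 0.31.
- Afferent: t0 is 3 to 5 ms. Collision ends at W + 3 to W + 5.

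| F (ms) | M (ms) | P (ms) | W (ms) | Efferent collision ends (ms) | Afferent collision ends (ms) |
|---|---|---|---|---|---|
| 24 | 4.5 | 13.75 | 9.25 | 8.45-8.94 | 12.25-14.25 |
| 24 | 3 | 13.00 | 10.00 | 9.20-9.69 | 13.00-15.00 |
| 28 | 3.5 | 15.25 | 11.75 | 10.95-11.44 | 14.75-16.75 |
| 32 | 4.5 | 17.75 | 13.25 | 12.45-12.94 | 16.25-18.25 |
| 32 | 3 | 17.00 | 14.00 | 13.20-13.69 | 17.00-19.00 |

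In every row the afferent volley can collide at all intervals from 0 to 10 ms. The second condition is met too: the antidromic volley reaches the cord no earlier than W = 9.25 ms, by which time a spike launched at 3-5 ms is already descending.

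**Wider check.** F 22-36 ms, M 2.5-5 ms, afferent delay 0.5-5 ms and interval 0-10 ms give 36,540 combinations. Efferent collision occurred in 35,420 and afferent collision in 36,461. In none did the efferent route collide without the afferent route. This follows from the formulas: whenever W exceeds the afferent delay, the efferent window lies inside the afferent one.

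**Where the routes differ.** The two end-points are 3 + 0.31 = 3.31 ms to 5 + 0.80 = 5.80 ms apart, just after the efferent window closes. For F 28 and M 3.5 that is about 11-17 ms. The gap depends on the delay. If the delay fell to 0.5 ms, the afferent window for the same subject would end at 12.25 ms, only 0.81-1.30 ms after the efferent one.

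**The case against.** The best defence has four parts.

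1. **Collision spares axons that CES did not fire.** The F-wave shock is supramaximal, at about 110-120% of the intensity for maximal CMAP, so abolishing F-responses requires CES to fire nearly all the motor neurons that produce them. CES near threshold need not do that. In motor neurons made more excitable but not fired, Hypothesis 1.2 predicts higher F-persistence. This stands: a reader might infer that the afferent route predicts an identical block, and the documents do not support that. A complete block points to broad recruitment. But the plan sets no completeness criterion, and broad recruitment is still not route.

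2. **The Interpretation is limited to high intensity, where independent support exists.** The Preliminary Data report latencies equal to or shorter than peripheral motor conduction time, and little or no decrement to a second pulse at 40 ms. This also stands. A reader might infer that a wholly reflex response at high intensity could pass as efferent; those data argue against it. What is missing is any link: the Interpretation does not make its conclusion depend on either measure, and the hypothesis has no intensity limit beyond suprathreshold.

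3. **Intervals beyond 10 ms are available.** A reader might infer that the study leaves out the intervals that separate the routes. The documents do not show that. The 10 ms is a predicted window; conditioning is allowed within 300 ms, and interstimulus interval is an ANOVA factor. Equally, nothing commits the study to those intervals or to comparing when the block ends.

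4. **The hypothesis is labelled speculative and is absent from the Specific Aims.** That limits its weight. The label concerns whether a block will be seen; the inference drawn from one is unhedged.

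**Conclusion.** The inference is too strong as written. An F-wave block at 0-10 ms shows that CES fired the blocked motor axons, not by which route. A complete block at high intensity, taken with the preliminary latency and paired-pulse findings, is consistent with efferent transmission, and that conclusion may well be true; the block alone does not demonstrate it.

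The exact end-points rest on assumed F and M latencies and conduction velocity. The overlap within 0-10 ms does not depend on them closely, although at the shortest assumed latencies the efferent window closes slightly before 10 ms. The 3-5 ms delay is an upper figure for APB at peri-threshold intensity. It may be shorter at higher intensity, and no value is given for FDI. No sample size, primary outcome or safety rule depends on this point; it affects what Aim 1 may conclude about mechanism.

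**What to change.** 1. **Reword and tie to latency.** Say that a block *would be consistent with* efferent transmission and collision. Claim the efferent route only at intensities where CES onset latency, in the same subject and muscle, is no longer than peripheral motor conduction time. Both are obtainable from planned recordings. Read CES latency from sweeps in which the wrist shock does not interfere: at a 10 ms interval with M 3.5 ms the M-wave starts at 13.5 ms, close to the CES response (P = 15.25 ms for F 28). A block at peri-threshold intensity limits the route claim at that intensity only and does not bar it at higher ones.

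2. **Add intervals.** Within the planned 0-300 ms range, include F-wave intervals of about 8-18 ms, placed around each subject's peripheral motor conduction time minus M-wave latency. Report the interval at which the block ends as supportive evidence only, because the afferent delay may shrink with intensity and refractoriness may prolong a block by either route.

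**Cost.** Each added condition needs 25 pulses at 0.1 Hz, 25 x 10 s = 250 s, or about 4 minutes. The conclusion becomes more cautious. No new participants or equipment are needed.
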